#### **7.9.1.2 Efficacy Analysis for the clinical response rate**

The clinical response rate will be analyzed using Logistic regression with treatment as fixed effects at Weeks 4 and 12. (Table 14.2.5)

The ROC curve will be created and cutoff number for responder will be calculated. (Figure 14.2.1)

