10.3.6 Analysis of secondary endpoints

After the main analyses for all co-primary endpoints successfully show the treatment effect, efficacy analyses for the secondary endpoints may be continued in a fixed order as deemed appropriate as follows.

1. The proportion of responders at Weeks 4 and 12 (i.e., subjects with cutoff number* or greater reduction in the average daily frequency of moderate and severe VMS compared to baseline).
2. Time to response, defined as time (in weeks) from randomization to the first time subjects meet responder criteria (i.e., cutoff number* or greater reduction from baseline in the average daily frequency of moderate and severe VMS).
3. Change from baseline to Weeks 4 and 12 in the ISI total score.

*Note: The cutoff number of responder criteria will be calculated using anchor-based method, using PGIC as the anchor. The satisfied subjects will be defined as those whose PGIC response is either 6 or 7. The cutoff number is defined as numerical value to maximize the sum of sensitivity and specificity for change from baseline in average daily frequency of moderate to severe VMS. This calculation will use weeks 4, 12 and 4 arms pooled data.

The proportion of responders will be analyzed using a logistic regression model with treatment as fixed effect and baseline as covariate.

The time to response will be analyzed with a log-rank test for each MT-8554 arm with placebo, with treatment as fixed effect and baseline as covariate. The VMS severity score and ISI will be analyzed using a procedure similar to the main analyses for co-primary endpoints.

Further details will be provided in the SAP.

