### 7.9.1 Primary Efficacy Analysis

Unless otherwise noted, these analyses are performed using ITT population.

In order to deal with multi-endpoints multiplicity, the primary efficacy analyses of primary and secondary endpoints will be judged to statistical significance in the order shown below.

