#### **7.9.1.3 Efficacy Analysis for the time to clinical response**

The Log-rank test will be used to analyze the time to clinical response. (Table 14.2.6) And Kaplan-Meier curves will be created. (Figure 14.2.2) For subjects who do not have reached to clinical response, treat their last visits as censoring.

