## 7.12 Statistical/Analytical issues

### 7.12.1 Adjustments of covariates

In the efficacy analysis, repeated measures ANCOVA model with an unstructured covariance structure or ANCOVA will be performed with baseline as a covariate in order to consider the impact of the baseline on the change in each variable. More details were described in each analysis.

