### 7.12.4 Multiple Comparison/Multiplicity

In order to deal with multi-endpoint multiplicity, the efficacy analyses of primary and secondary endpoints will be conducted in the order fixed method. The details are described in Section 7.9 Efficacy Assessments.

The secondary analysis of primary variable and the analysis of other efficacy endpoints are performed from the exploratory perspectives and therefore no adjustment will be made for the multiplicity among variables and time points.

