**8. CHANGES FROM THE PROTOCOL**

Subgroup analysis of antidepressant using (Y, N) will not be performed because there are not enough subjects with using antidepressant for the analysis.

Analysis for PP Population does not apply to secondary endpoints. These analyzes were considered to be excessive.

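### SAP 7.9.1.2 and 7.9.1.3 drop the baseline covariate that protocol 10.3.6 names for responder rate and time to response, and SAP Section 8 declares neither change

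*SAP*

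**What the plan says.** **Responder rate.** Protocol 10.3.6, repeated in the synopsis: "The proportion of responders will be analyzed using a logistic regression model with treatment as fixed effect and baseline as covariate". SAP 7.9.1.2: "The clinical response rate will be analyzed using Logistic regression with treatment as fixed effects at Weeks 4 and 12". Treatment is the only model term that the SAP names.

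**Time to response.** Protocol 10.3.6 asks for a "log-rank test for each MT-8554 arm with placebo, with treatment as fixed effect and baseline as covariate". SAP 7.9.1.3: "The Log-rank test will be used to analyze the time to clinical response". It adds Kaplan-Meier curves and a censoring rule, but names neither baseline nor the arms to be compared.

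**Place in the testing order.** SAP 7.9.1 says that "the primary efficacy analyses of primary and secondary endpoints will be judged to statistical significance in the order shown below", and SAP 7.12.4 that "the efficacy analyses of primary and secondary endpoints will be conducted in the order fixed method". The order is co-primary endpoints, responder rate, time to response, ISI.

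**Declared changes.** SAP Section 8 lists two: the antidepressant subgroup analysis is dropped, and "Analysis for PP Population does not apply to secondary endpoints". Neither concerns these models.

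**The concern.** Under SAP 5.4.3 a responder is a woman whose daily frequency of moderate to severe VMS falls by at least one fixed number. A reduction cannot exceed the baseline count, so women with more VMS at entry have more room to meet the criterion. Baseline is therefore likely to predict response, and leaving a predictive covariate out of a logistic model or a log-rank comparison usually costs power.

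The loss would fall on the first two secondary steps. If the order is applied strictly, a failure at either one stops formal testing of what follows. There is also a documentation problem. The two governing documents specify different analyses, and a reader cannot tell whether the SAP's version is intended. Settling that after unblinding would leave the analyst a choice that could have been closed beforehand.

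**Working it through.** **1. Does anything else in the SAP restore baseline?** SAP 7.12.1 says that "repeated measures ANCOVA model with an unstructured covariance structure or ANCOVA will be performed with baseline as a covariate". That covers the two ANCOVA families and refers to the individual analyses for detail; logistic regression and the log-rank test are not included. Elsewhere the SAP names baseline where it uses it: the co-primary model (7.9.1.1), ISI (7.9.1.4), and PSQI, MENQOL and SF-36 (7.9.3). Its absence from 7.9.1.2 cannot be read as implied.

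**2. Are the arm-versus-placebo comparisons supplied elsewhere?** SAP 7.9.2.1 plans placebo against each dose, using the same model, for endpoints with a significant treatment effect. It cites Section 7.9.1.1, which holds only the co-primary endpoints, but attaches the title of the whole of 7.9.1. Whether it reaches time to response is unclear.

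**3. Why baseline should matter.** Required percentage reduction = cutoff / baseline. The cutoff is to be estimated from trial data, so the documents give no value. With an assumed 4.5/day:
- baseline 7/day: 4.5 / 7 = 64%
- baseline 16/day: 4.5 / 16 = 28%

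**4. Size for responders.** The documents show no responder rates, cutoff or baseline-response correlation, so every input except 91 per arm (protocol 4.1) and two-sided 5% (SAP 5.2) is assumed:
- baseline lognormal, median 9.5/day, log-SD 0.20, 0.38 or 0.50
- placebo mean reduction 35%, SD 28 points; no dropout
- reduction = percent × [k × baseline + (1 − k) × 9.5], capped at baseline, with k = 0 (independent of baseline), 0.5 or 1 (proportional)
- cutoff 3, 4.5 or 6 per day
- active mean tuned to the stated unadjusted power; 2500 simulated trials per scenario, Week 12, one arm versus placebo

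Power gained by adding baseline to the logistic model, in percentage points:

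| Unadjusted power | k = 0 | k = 0.5 | k = 1 |
|---|---|---|---|
| about 70% | −0.5 to 1.1 | 0 to 6.8 | 0.6 to 11.7 |
| about 90% | −0.2 to 0.8 | 0.3 to 4.7 | 0.8 to 7.8 |

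Monte Carlo standard error of a gain is at most 0.9 points. Under the null the rejection rate was 3.8–5.5% unadjusted and 4.0–5.8% adjusted, so both tests hold their level. In the middle scenario (log-SD 0.38, k = 1, cutoff 4.5) power rose from 69.7% to 78.0%, and the odds ratio moved from 2.14 to 2.51.

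**5. How far the upper end rests on low baselines.** The lognormal above has no lower limit. At log-SD 0.50:
- share below 7/day = Φ(ln(7/9.5) / 0.50) = Φ(−0.61) = 27%
- share below 6/day = Φ(ln(6/9.5) / 0.50) = Φ(−0.92) = 18%; these women cannot respond at a cutoff of 6

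Inclusion criterion 3 asks for 7 or more per day (or 50 per week) in Screening. With baseline held at 7/day or more, the largest responder gain at about 70% unadjusted power falls from about 12 points to about 7. The analysis baseline is Day −7 to −1, after run-in, and criterion 6 tolerates a fall of up to 50% (7 × 0.5 = 3.5/day). The truth may lie between the two.

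**6. Responder step with four arms and both weeks.** The SAP does not say which doses and weeks must succeed. With k = 1 and no lower limit, the largest gain is 10.6 points if the 3-df test must succeed at both weeks, 11.7 if 10 mg must at both, 10.9 if any dose at either week suffices, and 2.9 if every dose must at both. With k = 0 it is within 1 point of zero in all four.

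**7. Time to response.** Log-rank stratified by baseline tertile versus plain, one arm versus placebo, about 70% unadjusted power, no lower limit: −1.7 to 3.0 points (k = 0), −2.0 to 10.1 (k = 0.5), 0.1 to 18.2 (k = 1). A smaller run at k = 1 with log-SD 0.38 and 0.50 (600 trials per cell, unadjusted power roughly 55–80%) gave 3 to 20 points without the limit and 0 to 11 with baseline at 7/day or more.

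**The case against.** Several points on the other side stand.

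- A standard log-rank test has no covariate term, so the protocol's sentence for time to response cannot be run as written. The SAP kept the part that can be run, and the protocol leaves further details to the SAP. Stratifying can also cost up to 2 points when baseline matters little. This half of the point is the weaker one. The argument does not reach the logistic model, which runs exactly as the protocol words it; removing a named covariate there is a change, not a detail.
- Protocol 10.3.1 sends deviations from the planned analysis to a separate document and the study report, not to SAP Section 8. A reader might infer that the changes were never justified anywhere. The documents do not show that; they show only that the SAP's own list of changes omits them.
- A reader might infer that the SAP has no placebo comparison for time to response. That is too strong: SAP 7.9.2.1 may be meant to supply it, but its scope is ambiguous.
- A reader might take 12 or 18 points as the expected loss. Those are upper ends that require proportional reduction, widely spread baselines and a sizeable share of women below 7/day. They also concern one arm versus placebo, while the SAP's step may be an overall treatment test. No four-arm figure is available for time to response.
- Protocol 10.3.6 makes the secondary sequence optional, so the cost of failing a step depends on how strictly the order is applied.
- Adding baseline changes the odds ratio from marginal to conditional. This is a real but small downside, and labelling deals with it.

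**Conclusion.** The mismatch is certain; its cost is not. The SAP omits baseline from both analyses, nothing else in it puts baseline back, and Section 8 is silent. A reader might infer that the unadjusted tests are invalid or that the primary result is at risk. Neither follows: type I error is held and the co-primary models already carry baseline.

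The cost is possible lost power in the first two secondary steps. For responders, with one arm versus placebo, 91 per arm and about 70% unadjusted power, the loss is about zero if the reduction does not depend on baseline. If the reduction is proportional to baseline, the loss is up to about 7 points with baseline at 7/day or more and up to about 12 without that limit. These are ranges over assumed inputs, not an expected loss. For time to response, the need is to reconcile the two documents; the power argument there is less secure.

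**What to change.** **SAP 7.9.1.2.** Specify logistic regression with treatment as fixed effect and baseline average daily frequency of moderate to severe VMS as covariate. The protocol says only baseline; this is its natural reading. Label the odds ratio as conditional on baseline.

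**SAP 7.9.1.3.** Reconcile with protocol 10.3.6 in one of two ways. Either name one method that can carry baseline, for example a log-rank test stratified by baseline frequency or a Cox model with treatment and baseline (stating how ties are handled, since times are whole weeks). Or keep the plain log-rank test and declare it in Section 8. In either case state whether the comparisons of each MT-8554 arm with placebo belong to 7.9.1.3 or to 7.9.2.1, and correct the cross-reference in 7.9.2.1, which by number points only to 7.9.1.1.

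**SAP Section 8.** If the unadjusted responder analysis is intended, list it and give the reason.

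The cost is a phrase in each subsection and one model term or stratification factor. Baseline frequency is already derived under SAP 5.4.1, so no new data are needed. The change should be made before unblinding.

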#### **7.9.1.3 Efficacy Analysis for the time to clinical response**

The Log-rank test will be used to analyze the time to clinical response. (Table 14.2.6) And Kaplan-Meier curves will be created. (Figure 14.2.2) For subjects who do not have reached to clinical response, treat their last visits as censoring.

#### **7.9.1.4 Efficacy Analysis for the Insomnia Severity Index**

The change from baseline to Weeks 4 and 12 in the ISI total score will be analyzed using ANCOVA model with treatment as fixed effects and baseline value as covariate (Table 14.2.7.1). In addition, ISI Total Score in categories will be summarized for each visit (Table 14.2.7.2). The following categories will be used for the analysis;

- No clinical significant insomnia: ISI total score 0 – 7
- Subthreshold insomnia: ISI total score = 8 – 14
- Clinical insomnia (moderate): ISI total score = 15 – 21
- Clinical insomnia (severe): ISI total score = 22 – 28

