10.3.5 Analysis of primary endpoints

Main Analysis

Change from baseline to Week 4 and Week 12 in the average daily frequency of moderate to severe VMS will be analyzed using a repeated measures analysis of covariance (ANCOVA) model with an unstructured covariance structure. The analysis model will include baseline value of the endpoint as a covariate; weeks, treatment, antidepressant using (Y,N), and interaction between antidepressant using (Y,N) and treatment as fixed effect. Relevant covariates will also be included in the model. If the normality assumption for the model is not met, a non-parametric method such as a ranked analysis of variance (ANOVA) will be performed.

The sensitivity analysis will be conducted using primary analysis model with applicable covariates for ITT subjects without using antidepressants.

Similar analyses will be conducted for VMS severity.

Comparison between each dose of MT-8554 and placebo will also be conducted using a repeated measures ANCOVA model. Point estimates and 95% CIs for the difference between each active dose and placebo will be obtained.

Further details will be provided in the SAP.

Secondary Analysis

The primary endpoints will also be analyzed using Maximum Contrast Methods with baseline value of the endpoint as a covariate, or slope approach¹³, as an analysis of the dose-response relationship. The detail will be specified in the SAP.

The primary endpoints will also be analyzed using an ANCOVA model.

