**Table 5 Derived Analysis Visit Windows**

	Nominal day	Window
Baseline	NA	NA
Day 1	Day 1 (First dose day)	NA
Week 2	Day 15	Day 7 to 21
Week 4	29	Day 22 to 42
Week 8	57	Day 43 to 70
Week 12	85	Day 71 to 98
Week 16 (FU)	115	NA

The analysis visits are derived according to the following criteria:

- The unscheduled visits are not used for the deriving.
- If a study visit is the only one in an analysis window, this study visit becomes the derived analysis visit.
- If there are multiple visits in a visit window, the closest visit to the nominal day becomes the analysis visit. In the event that two visits are the closest visits to the nominal day and equally distanced to the nominal day, the visit after the nominal day becomes the derived visit.
- The follow-up visit will not be derived. The study visit will be used.
- Unscheduled visits and retests (same visit number assigned), will not be displayed in by-visit summary tables, but will be included in the data listings. All data will be listed. Listings will include treatment, scheduled, unscheduled, retest and early discontinuation data.
- The screening and run-in visits are carried to derived visits
- The efficacy endpoints based on diary data use different windows. See Section 5.4.1.

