### 7.12.2 Data Handling of Dropouts or Missing

Missing data will not be imputed in the summary at each time point. The missing data will not be imputed for efficacy analyses. For AE start and/or end date missing or partial missing, the AE will be treated as TEAE if it cannot be determined a non-TEAE.

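### The SAP tests the Insomnia Severity Index with a plain ANCOVA instead of the protocol's repeated-measures approach, does not declare the change, and leaves the Week 12 result open to bias if withdrawal depends on Week 4 ISI

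*SAP*

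**What the plan says.** Protocol 10.3.6 places the change in ISI total score third and last in the fixed order of secondary endpoints. On method it says: "The VMS severity score and ISI will be analyzed using a procedure similar to the main analyses for co-primary endpoints". The main analysis it points to, in protocol 10.3.5, is carried out "using a repeated measures analysis of covariance (ANCOVA) model with an unstructured covariance structure".

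SAP 7.9.1.4 says: "The change from baseline to Weeks 4 and 12 in the ISI total score will be analyzed using ANCOVA model with treatment as fixed effects", with the baseline value as covariate. It names no visit term and no within-subject covariance. On missing values, SAP 7.12.2 says: "The missing data will not be imputed for efficacy analyses".

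ISI is scheduled after randomization at Week 4 and at the EOT visit, which is Week 12 or early termination (protocol 5.2.3.3 and 5.2.3.5). SAP Table 5 assigns visits to analysis weeks by study day: Week 4 is Day 22 to 42, Week 8 is Day 43 to 70, and Week 12 is Day 71 to 98. Where a window holds several visits, "the closest visit to the nominal day becomes the analysis visit".

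SAP Section 8 declares two changes from the protocol. One drops the antidepressant subgroup. The other is: "Analysis for PP Population does not apply to secondary endpoints". The ISI model is not mentioned.

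**The concern.** The two documents give different main analyses for an endpoint in the testing sequence, and the difference matters when data are missing. A repeated-measures model fits Weeks 4 and 12 jointly, so a woman seen only at Week 4 still informs the Week 12 estimate through the correlation between visits. A plain ANCOVA at Week 12 uses only women with a Week 12 value.

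Subjective sleep quality is a stated secondary objective, and ISI is the only sleep measure in the fixed order (PSQI is listed among the other endpoints). If women whose sleep is poor at Week 4 leave one arm more than another, those who remain at Week 12 are selected differently by arm and the comparison shifts. SAP 7.9.4 has no missing-data sensitivity analysis for ISI that would show this.

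**Working it through.** **1. Are the two models really different?** The SAP treats them as alternatives. Section 7.12.1 says: "repeated measures ANCOVA model with an unstructured covariance structure or ANCOVA will be performed with baseline as a covariate". For the co-primary endpoints, 7.9.1.1 uses the repeated-measures model as the main analysis, and 7.9.4 uses a plain ANCOVA at Weeks 4 and 12 as a sensitivity analysis. For ISI, the plain ANCOVA is the only model. That it is fitted separately at each visit is an inference from the missing visit term and from this contrast.

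**2. Where does an early-termination ISI go?** Take an EOT visit after the nominal Week 4 visit and before Day 85, that is Day 30 to 84 (55 days), and apply Table 5:

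| EOT day | Days | Analysis week | Used in the Week 12 test? |
|---|---|---|---|
| 30–42 | 13 | Week 4 | No |
| 43–70 | 28 | Week 8, no ISI model planned | No |
| 71–84 | 14 | Week 12 | Yes |

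The value misses the Week 12 test on 13 + 28 = 41 of 55 days and enters it on 14 of 55 (25%). These are calendar days, not shares of women. On Day 30 to 42 the EOT usually loses to the Week 4 visit but not always. If Visit 5 was on Day 26, an EOT on Day 30 or 31 is nearer Day 29, and on Day 32 the tie goes to the later visit. Either way the value counts as Week 4.

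**3. How large could the bias be?** The plan's one relevant figure, 4 × 91 = 364 randomized, reproduces. No ISI effect, SD, correlation or dropout rate is visible, so these are assumptions: residual SD σ = 5 points, Week 4–Week 12 correlation ρ = 0.65, true difference −1.5 points, and every woman who drops out after Week 4 lacks a Week 12 value. The log-odds of dropout rise by s per SD of Week 4 residual z (positive is worse), and dropout rates are quoted at an average Week 4 score.

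The bias of the Week 12 ANCOVA is approximately ρ × σ × (mean z of active stayers − mean z of placebo stayers). A negative value favors active.

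- Dropout 10% placebo, 25% active, s = 1: mean z of stayers −0.119 and −0.242. Bias = 0.65 × 5 × (−0.2417 + 0.1193) = −0.40.
- Dropout 10% placebo, 20% active, s = 0.7: mean z −0.078 and −0.143. Bias = 0.65 × 5 × (−0.1430 + 0.0779) = −0.21.

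A simulation of 4,000 two-arm trials with 91 per arm agrees:

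| Dropout, placebo vs active | ANCOVA bias (SE) | Repeated-measures bias (SE) |
|---|---|---|
| 10% vs 25%, s = 1 | −0.38 (0.83) | 0.02 (0.81) |
| 10% vs 20%, s = 0.7 | −0.21 (0.81) | 0.00 (0.79) |
| 15% vs 15%, random | 0.02 (0.81) | 0.02 (0.78) |

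The first two biases are 0.38/1.5 = 25% and 0.21/1.5 = 14% of the assumed effect. The 0.02 values are within Monte Carlo error, since 0.8/√4000 is about 0.013.

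**4. When does bias arise, and in which direction?** A large-sample simulation (200,000 per arm, ρ from 0.5 to 0.8, s = 1, overall dropout 10% to 25%) gives, in SD units:

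| Withdrawal pattern (placebo vs active) | ANCOVA | Repeated measures |
|---|---|---|
| Unrelated to outcome, equal or unequal rates | within 0.006 | within 0.006 |
| Depends on Week 4 ISI in both arms, 10% vs 10% | within 0.004 | within 0.003 |
| Same, 10% vs 20% | −0.047 to −0.066 | within 0.006 |
| Same, 25% vs 10% | +0.061 to +0.099 | within 0.001 |
| Depends on Week 4 ISI in placebo only | +0.042 to +0.170 | within 0.007 |
| Depends on unseen Week 12 ISI, unequal rates | 0.075 to 0.120 in size | 0.029 to 0.088 in size |

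**The case against.** The protocol asks for a similar procedure, not an identical one, and leaves detail to the SAP. SAP 7.12.1 provides for either model. ISI is last in the order, so no later test depends on it, and this is a Phase II dose-selection study. Women who stop drug are to be kept on study (protocol 4.5.1 and 5.2.3), which limits missing data. Even the larger bias above is under half a standard error (0.38/0.83 = 0.46).

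Most of this bears on size, and it stands. It does not remove the discrepancy: a model without within-subject covariance lacks the feature that sets the co-primary analysis apart, and Section 8 is where the SAP lists its changes.

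A reader might infer more than the documents support:

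- That every woman who withdraws after Week 4 is lost to the Week 12 test. She is not: an EOT visit from Day 71 counts as Week 12.
- That unequal withdrawal by itself causes bias. It does not: unequal rates unrelated to outcome gave none, and neither did the same Week 4 dependence at equal rates.
- That the bias must flatter MT-8554. It reverses when placebo loses more women.

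**Conclusion.** The concern holds in limited form. SAP 7.9.1.4 departs from protocol 10.3.6 without declaring it in Section 8, and a woman with no ISI on Day 71 to 98 is left out of the Week 12 test although her Week 4 value could inform it. The Week 12 comparison can be biased, in either direction, if withdrawal depends on Week 4 ISI and that dependence or the withdrawal rate differs by arm.

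The size is about 0.2 to 0.4 ISI points, and it rests wholly on the assumed SD, correlation, dropout rates and strength of dependence. It also takes every dropout to lack a Week 12 value, which overstates the loss where an EOT visit falls on Day 71 or later. The departure from the protocol is a matter of text and needs no assumption.

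Repeated measures is not a complete cure. It removes the bias when missingness depends on observed values, and only reduces it when withdrawal depends on unobserved Week 12 ISI. It was at least as precise as the ANCOVA in the trials simulated here.

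**What to change.** In SAP 7.9.1.4, make the main ISI analysis a repeated-measures ANCOVA of change from baseline at Weeks 4 and 12 with unstructured covariance, in the form of SAP 7.9.1.1: treatment, visit, treatment-by-visit, baseline and baseline-by-visit, with the antidepressant terms handled as for the co-primaries. This follows the protocol's approach but is not its literal model, because protocol 10.3.5 lists neither visit interaction. Keep the plain ANCOVA at each visit as a sensitivity analysis.

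If the plain ANCOVA stays as the main analysis, declare and justify it in Section 8 and add a missing-data sensitivity analysis for ISI.

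The cost is one SAP paragraph and a small amount of programming. No new data are needed.
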